2.1. Sample Size Calculation

In order to determine the number of samples, power analysis was performed using the G*Power (v3.1.9.2) program. The power of the study is expressed as $1-\beta$ (β = probability of type II error). Based on the postoperative 6th-hour pain measurements in the article by D. Liapis et al.*, the mean for Group I was 13.9 SD:16.2; When the mean for Group II was taken as 4.9 SD: 7.3, the effect size (d) was found to be 0.716 in the calculation made to obtain 90% power at the $\alpha=0.05$ level. Accordingly, it was calculated that there should be at least 42 people in each group and 84 people in total. Considering that there may be losses during the study process (20%), it was decided to take at least 50 people in each group.

10 patients will be involved in a pilot study. There will be 5 patients in each group: manual final irrigation and EndoClean device. Pilot study will be conducted for two reasons. The first reason is to ensure the safety of the device for clinical use. The second reason is to conduct an accurate power analysis and therefore, a sample group for the full clinical study. A full clinical investigation will be performed once the pilot study is done, and which will be powered according to the outcome of the pilot study.

3. Objectives

The primary objective of this randomized controlled trial is to compare the postoperative pain intensity levels in patients with asymptomatic teeth diagnosed for non-surgical orthograde root canal treatment that are disinfected during the root canal treatment procedure by manual irrigation with

sodium hypochlorite (NaOCl) solution or EndoClean. The secondary objective is to evaluate, if EndoClean could be used safely during root canal treatment as an alternative approach to manual irrigation.

4. Outcomes

4.1 Primary Outcome: All participants will be asked to grade their pain intensity level on a horizontal Visual Analogue Scale (VAS) before the treatment procedure. This scale is a horizontal 100 mm bar, marked in every 10mm with two ends. One end (0) indicated “no pain” and the other end (10) indicated “worst pain possible”. Categorization of pain scores is as follows: 0-4 mm = No Pain, 5-44 mm = Mild Pain, 45-74 mm = Moderate Pain, 75-100 mm = severe pain. After grading the pain level, the distance between the marked point and the “no pain” endpoint will be measured with a ruler to calculate the pain intensity level. Clinical and radiological findings consistent with the asymptomatic tooth with nonvital pulp tissue with the preoperative pain intensity scores in the category of “no pain” will be included in the study.

4.2 Secondary Outcome: If excessive pain will be experienced by three concomitant patients the study will be terminated.

5. Populations to be Analysed

Data of all randomised study subjects will be analysed. This will be seen as the primary population for the analysis. For any specific analysis, study subjects with missing data on any of the variables in the model will be excluded from the analysis.

6. Analyses

All outcomes will be presented using descriptive statistics; normally distributed data by the mean and standard deviation (SD) and skewed distributions by the median and interquartile range (IQR). Binary and categorical variables will be presented using counts and percentages. Python programming language and its dependent statical libraries will be used for all statistical analysis.

The subsections below will describe analyses in addition to the descriptive statistics.

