3.3.1.1. Sample Size Calculation

In order to determine the number of samples, power analysis was performed using the G*Power (v3.1.9.2) program. The power of the study is expressed as $1-\beta$ (β = probability of type II error). Based on the postoperative 6th-hour pain measurements in the article by D. Liapis et al.*, the mean for

Group I was 13.9 SD:16.2; When the mean for Group II was taken as 4.9 SD: 7.3, the effect size (d) was found to be 0.716 in the calculation made to obtain 90% power at the $\alpha=0.05$ level. Accordingly, it was calculated that there should be at least 42 people in each group and 84 people in total. Considering that there may be losses during the study process (20%), it was decided to take at least 50 people in each group.

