3.3.1.2. Pilot Study

10 patients will be involved in a pilot study. There will be 5 patients in each group: manual final irrigation and EndoClean device. Pilot study will be conducted for two reasons. The first reason is to ensure the safety of the device for clinical use. Thesecond reason is to conduct an accurate power analysis and therefore, a sample group for the full clinical study. A full clinical investigation will be performed once the pilot study is done, and which will be powered according to the outcome of the pilot study.

3.3.1.3. Inclusion Criteria:

1. Physical status classification system described was used for patients' recruitment. Healthy patients, who were classified by the American Society of Anaesthesiologists (ASA) as ASA I and II
2. Patients with the age of 18 and over
3. Patients who were diagnosed as in need of non-surgical orthograde root canal treatment of an asymptomatic tooth
4. Tooth without signs of previously initiated Root Canal Therapy

3.3.1.4. Exclusion Criteria:

1. Pregnant and lactating females
2. Patients with chronic periodontal diseases
3. Patients with sensitivity or adverse reactions to any medication or materials that were used throughout the treatment procedure
4. Patients with acute periapical periodontitis
5. Patients with acute periodontal abscess
6. Patients who could not abide by the follow-up time
7. Patients who used analgesics 1-week prior or antibiotics 1-month prior to treatment
8. Uncooperative patients
9. Teeth that cannot be made functional nor restored or difficult to access teeth with no importance (wisdom teeth)
10. Teeth with poor prognosis, for example, due to deep root caries or big root resorption
11. Teeth with ≥ 4 mm periodontal pocket depth
12. Teeth with an inaccessible root end
13. Teeth with apical resorption or a radiologically not clearly defined apex
14. Fractured teeth
15. Teeth with immature or open apices
16. Teeth with root apices extending into the maxillary sinus

17. Teeth with external resorption communicating with the pulp

3.3.1.5. Withdrawal Criteria:

Subjects may be withdrawn from the study at the discretion of the Investigator or Sponsor due to a safety concern or if judged non-compliant with trial procedures.

A subject must be withdrawn from treatment if one of the following applies:

- Subject chooses to withdraw from the study at any time;
- Intolerable adverse effects;

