Statistical analysis will be defined on later stage. It is a pilot study with exploratory statistics.

12. Financing and Insurance

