6.1 Outcome

The primary analysis will compare the treatment groups [EndoClean and manual irrigation with sodium hypochlorite (NaOCl)] on their mean difference in post-operative pain sensitivity throughout a week period (6h, 24h, 48h, 72h and 1w). Declared pain scores over time for the patients will be the dependent variable. Study subjects will be considered as random effects, treatment group and visit number as fixed effects. Other variables like Age and Toot-ID can be included as a covariate according to their relations with response variable. The estimated difference in mean change from EndoClean and Control groups and the corresponding 95 % confidence interval (CI) will be presented.

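### Fifty per group leaves 40, not the required 42, after the plan's own 20% loss (a small slip), and the plan does not say whether 50 still binds once a 5-per-arm pilot re-powers the study

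*SAP*

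**What the plan says.** SAP 2.1 and Protocol 3.3.1.1 carry the same calculation. It takes 6-hour pain from a published study, with means 13.9 and 4.9, SDs 16.2 and 7.3, and d = 0.716. The target is 90% power at alpha 0.05, and the result is that "it was calculated that there should be at least 42 people in each group and 84 people in total". The allowance for losses follows: "Considering that there may be losses during the study process (20%), it was decided to take at least 50 people in each group".

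SAP 2.1 (next paragraph) and Protocol 3.3.1.2 then describe a 10-patient pilot, 5 per group, meant partly to supply an accurate power analysis. After it comes the main study: "A full clinical investigation will be performed once the pilot study is done", "which will be powered according to the outcome of the pilot study".

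Three other places bear on the point:

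- SAP 5 on missing data: "For any specific analysis, study subjects with missing data on any of the variables in the model will be excluded from the analysis".
- SAP 6.1 on the primary model, which uses all five post-treatment times: "Study subjects will be considered as random effects, treatment group and visit number as fixed effects".
- Protocol 11 on the status of the study: "It is a pilot study with exploratory statistics".

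**The concern.** There are two separate matters.

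**(a) Loss allowance.** The plan names a required number, a loss rate and an enrolment minimum, and the three do not fit together. Because SAP 5 removes subjects with missing model data, losses do reduce the number analysed. A reader who relies on 90% power after 20% loss does not get it at the stated minimum.

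**(b) Two bases for one sample size.** The number is first fixed from published data with a minimum of 50 per group. The next paragraph hands the powering to the pilot. Neither document says which quantity the pilot re-estimates, how the number would change, or whether 50 still holds. If 50 is not a minimum, a very imprecise 10-patient result could set the size of the trial, and could set it too low.

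**Working it through.** **Inputs** (SAP 2.1, Protocol 3.3.1.1 and 3.3.1.2): means 13.9 and 4.9; SDs 16.2 and 7.3; alpha 0.05; power 90%; loss 20%; enrolment minimum 50 per group; pilot 5 per group. The documents do not state whether the test is one- or two-sided. A two-sided test reproduces 42 and a one-sided test gives about 35, so two-sided is used here.

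**Step 1. Reproduce the plan's figure.**

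- Difference = 13.9 − 4.9 = 9.0.
- Pooled SD = √((16.2² + 7.3²)/2) = 12.564.
- d = 9.0/12.564 = 0.716, as stated.
- Two-sample t-test (noncentral t): 42 per group gives 90.0% power. The plan's 42 is correct.

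**Step 2. Apply the plan's loss rate.**

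- 50 × (1 − 0.20) = 40 per group, 2 short of 42.
- Largest loss that still leaves 42: 1 − 42/50 = 16%.
- Enrolment needed for 42 after 20% loss: 42/0.80 = 52.5, so 53.
- The shortcut of adding 20% to the required number does not quite give 50 either: 42 × 1.20 = 50.4, so 51.

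**Step 3. Power at each number per group** (same test, normal scores).

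| Analysed per group | Power |
|---|---|
| 40 (50 enrolled, 20% lost) | 88.6% |
| 42 (50 enrolled, 16% lost) | 90.0% |
| 50 (no loss) | 94.4% |

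The shortfall at 20% loss is 90.0 − 88.6 = 1.4 points.

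**Step 4. Precision of a 5-per-arm pilot.** Suppose the pilot reproduced the planning values exactly.

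- SE of the difference = 12.564 × √(2/5) = 7.95.
- 95% CI assuming equal variances (8 df, t = 2.306): 9 ± 2.306 × 7.95 = −9.3 to 27.3.
- The planning SDs differ by more than a factor of two, so the Welch interval is also relevant. It has about 5.6 df and t = 2.495: 9 ± 2.495 × 7.95 = −10.8 to 28.8.
- 95% CI for the pooled SD (8 df, equal variances, normal scores): 12.564 × 0.675 to 12.564 × 1.916 = 8.5 to 24.1.
- Number per arm for a 9-point difference at 90% power: 20 at SD 8.5 and 152 at SD 24.1.

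On either variance assumption, the pilot could not tell a large benefit from a sizeable harm. Its SD alone would be compatible with sample sizes from under half of 42 to more than three times it.

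**The case against.** **On (a).** The effect is small. With no loss, 50 per group gives 94.4%, and the wording sets a minimum, so enrolling 53 already complies. The 1.4 points also depend on normal scores. In a simulation with assumed gamma-distributed scores that have the same means and SDs, 40 per group gave about 94%. Finally, the primary analysis is the repeated-measures model in SAP 6.1, for which no power is stated, so 88.6% is not the power of the primary analysis. All of this stands. It limits (a) to a minor correction, but the three stated figures still do not agree.

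**On (b).** The 50 is already worded as a minimum, and nothing says the pilot may lower it. One can also read the present plan as covering only the pilot, since Protocol 11 calls it exploratory, with the full study to be sized in a later plan. Against that second reading, the minimum of 50 and the 90% power stand in the current documents beside a formal null hypothesis. Neither reading is settled by the text, so confidence in (b) is moderate.

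**A stronger reading to avoid.** A reader might infer that the plan permits fewer than 50 per group, or that an under-sized trial is likely. The documents do not support this. They are silent on the matter, and silence is not permission. Simulation can illustrate the risk: with no minimum and normal scores, about 39% to 46% of such pilots would give a number with true power below 80%. Those shares rest on re-sizing rules that had to be assumed because the plan gives none. They also show only the low side, although the pilot could equally push the number up. They should not carry the severity.

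**Conclusion.** **(a) Wrong as written, certain, minor.** The stated minimum leaves 40 per group after the stated loss, where 42 are required. The cost is 1.4 points of power (88.6% against 90%) for the two-sided 6-hour t-test with normal scores. Meeting both stated figures would take 53 per group.

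**(b) A real inconsistency in the planning basis, moderate confidence.** The plan fixes a minimum and then says the pilot will power the study, without saying how the two fit together. A pilot of 5 per arm cannot set the sample size: its interval for the 9-point difference would run from about −9 to 27 with equal variances, or about −11 to 29 by Welch. Its SD interval implies roughly 20 to 152 per arm. These figures assume that the pilot returns the planning values; the SD range also assumes equal variances and normal scores. If 50 is meant to bind, the risk of under-sizing from the pilot goes away, and any upward change still needs a rule.

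**What to change.** **For (a)**, in SAP 2.1 and Protocol 3.3.1.1: state that 50 per group keeps 90% power up to 16% loss, and that at 20% loss (40 per group) planning power is 88.6%. Say that this refers to the two-sided 6-hour t-test and not to the repeated-measures model in SAP 6.1.

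**For (b)**, in SAP 2.1 and Protocol 3.3.1.2: state that the pilot cannot lower the sample size below 50 per group, or delete the sentence that re-powers the study from the pilot. If the pilot may raise the number, state which quantity is re-estimated, for example the SD only.

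**Clarification notes for the same edit:** say whether the 10 pilot patients count towards the 100 and belong to the SAP 5 population, and reconcile the exploratory label in Protocol 11 with the formal hypothesis and the 90% power.

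**Cost:** wording only, with no added patients if 50 per group is kept. Holding 90% power at the full 20% loss would instead take 53 per group, which is 2 × 3 = 6 more patients.

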3.4. Diagnosis

The patient's dental and medical history, demographic data (age, gender) are recorded and a thorough clinical examination, as well as radiological examination, is performed. During clinical examination, the relevant tooth, and surrounding tissues, as well as adjacent lymph nodes, are examined. Percussion and palpation tests, and periodontal probing of the relevant tooth are performed. A cold test (Roeko Endo-Frost, Coltène/Whaledent Langenau, Germany) is used to assess sensitivity. Periapical radiographs (KODAK RVG 5100, Carestream Health, Rochester, NY, USA) are produced with a paralleling technique for evaluation of periradicular tissues (exposure time: 0.16 s, exposure dose: 1.22 mGy). All findings of patients will be recorded in patients' charts.

After being trained by a blinded investigator, all participants will be asked to grade their pain intensity level on a horizontal Visual Analogue Scale (VAS) before the treatment procedure. This scale is a horizontal 100 mm bar, marked in every 10mm with two ends. One end (0) indicated "no pain" and the other end (10) indicated "worst pain possible". Categorization of pain scores is as follows: 0-4 mm = No Pain, 5-44 mm = Mild Pain, 45-74 mm = Moderate Pain, 75-100 mm = severe pain. After grading the pain level, the distance between the marked point and the "no pain" endpoint will be measured with a ruler to calculate the pain intensity level. Clinical and radiological findings consistent with the asymptomatic tooth with nonvital pulp tissue with the preoperative pain intensity scores in the category of "no pain" will be included in the study. (**Eyüboğlu & Kim 2020**).

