6.2. Post-endodontic pain assessment

After the treatment, all participants will be provided with analgesics (75 mg diclofenac sodium) (Voltaren SR 75 mg, Novartis, Kurtköy, İstanbul) and will be advised to use them if needs be and record the time of use. A pain intensity evaluation diary including VAS diagrams with their respective follow-up evaluation times will be provided to each participant to mark their pain. All participants will be contacted on their follow-up time to remind them to mark their pain intensity scores. Pain intensity of patients will be evaluated at 6h, 24h, 48h, 72h and 1 week after the completion of root canal treatment as previously described. Any complication such as paraesthesia, acute exacerbations, flare-ups, swellings will be also recorded on patients' charts. Patients who fail to abide by the follow-up time will be traced via phone, e-mail or SMS to determine the possible reasons for dropout.

7. Concomitant Treatments

Medications given to patients are to be documented

8. Schedule

The duration of the investigation and the post-assessment has to be justified.

Study duration:

Step 1. Patients enrollement: 2 months

Step 2. Treatment duration: 1 visit to dentist

Step 3. Follow-up period: 1 week

Flow chart of the study:

Investigation Periods	Consent (ICF) Screening	Treatment	Follow-up				
Visit	1 On-site	2 On-site	3	4	5	6	7 On-site
Time (hour, day, week)	-1 week	0	6 hours	24 hours	48 hours	72 hours	1 week
Patient consent (ICF)	x						
Demographics	x						
Medical History	x						
In- /Exclusion Criteria	x	x					
Dental Examination	x						x
X-ray		x					
Randomization		x					
Medical device application		x					
Concomitant Therapy,	x	x	x	x	x	x	x
(Serious) Adverse Events, Adverse device effects	x	x	x	x	x	x	x
Pain intensity			x	x	x	x	x
Pain intensity diary dispensing		x					
Pain intensity diary collection							x

9. Reporting of Unexpected Serious Adverse Events, Serious Adverse Events and Adverse Events

Unexpected Serious Adverse Events and Serious Adverse Events must be reported to the sponsor within 24 hours after awareness of the event by the Investigator. Unexpected Serious Adverse Events must be reported to the Ethics Committee and Regulatory Authority within identified timeline as per the regulations.

10. Premature Termination of the Study

If excessive pain will be experienced by three concomitant patients the study will be terminated.

11. Statistical Analysis

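### As worded, SAP section 5 drops a whole subject for one blank diary entry and discards four observed pain scores that the planned mixed model can use; exclusion should be by visit

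*SAP*

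**What the plan says.** SAP section 5 opens with the analysis population: "Data of all randomised study subjects will be analysed". It then adds the missing-data rule: "For any specific analysis, study subjects with missing data on any of the variables in the model will be excluded from the analysis". The unit excluded is the subject, not the visit or the data record.

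SAP section 6.1 defines the outcome: "Declared pain scores over time for the patients will be the dependent variable". The scores are those at 6 h, 24 h, 48 h, 72 h and 1 week. On the model it says: "Study subjects will be considered as random effects, treatment group and visit number as fixed effects". The pain score is thus one of the model's variables, and each subject should supply five values of it.

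Protocol section 6.2 has patients mark the scores themselves in a diary, with a safeguard: "All participants will be contacted on their follow-up time to remind them to mark their pain intensity scores". The flow chart in Protocol section 8 places "Pain intensity diary collection" at the on-site visit at 1 week.

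Protocol section 11 leaves the analysis to a later stage, so the SAP is the only place where the rule can be settled.

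**The concern.** A random-subject model does not need complete diaries. A subject with four of five scores still informs the treatment comparison. Applied literally, the rule removes that subject altogether, which sits poorly with the aim of analysing everyone randomised.

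Two things are at stake. The first is precision: observed scores are thrown away and the interval for the week-long difference widens. The second is bias: if patients with more early pain leave more later entries blank, the complete diaries are a selected set.

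The two possible units of exclusion also give different analysis sets from the same data, so the choice should not be left until the data are seen.

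**Working it through.** **Inputs from the documents.** Five scores per subject (SAP 6.1); 5 per arm in the pilot and at least 50 per arm planned (SAP 2.1); means and SDs of 13.9 (16.2) and 4.9 (7.3) at 6 h (SAP 2.1).

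**Assumed, because the documents give no value.** Blank rate m per visit of 2%, 5% or 10%; correlation ρ between a subject's scores of 0.3 to 0.8.

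**1. The plan's own figure.** Pooled SD = √((16.2² + 7.3²)/2) = 12.56, and d = (13.9 − 4.9)/12.56 = 0.716. A two-sided t-test at 0.05 with 90% power needs 42 per group. Both figures agree with SAP 2.1.

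**2. Pilot, no rate assumed.** 10 subjects × 5 = 50 scores. With one blank:
- dropping the visit leaves 50 − 1 = 49 scores from 10 subjects;
- dropping the subject leaves 50 − 5 = 45 scores from 9 subjects, so one arm loses 1 of 5 (20%).

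**3. What a four-score subject is worth.** With equal correlation, a subject with k scores carries information k/(1 + (k − 1)ρ) on the group effect. At ρ = 0.5 this is 4/2.5 = 1.60 against 5/3 = 1.67, or 96% of a full subject. The literal rule sets it to zero.

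**4. Complete diaries per arm.** If all 50 are returned and gaps are independent, the expected number is 50(1 − m)⁵. If 45 are returned, replace 50 by 45.

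| m | complete of 50 | complete of 45 |
|---|---|---|
| 2% | 45.2 | 40.7 |
| 5% | 38.7 | 34.8 |
| 10% | 29.5 | 26.6 |

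**5. Interval width.** At ρ = 0.5, information relative to complete data is 0.996, 0.990 and 0.978 when visits are dropped (average of step 3 over the number of scores present), and 0.904, 0.774 and 0.590 when subjects are dropped. The width ratio is the square root of their quotient:
- 2%: √(0.996/0.904) = 1.05
- 5%: √(0.990/0.774) = 1.13
- 10%: √(0.978/0.590) = 1.29

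The full treatment-plus-visit model, summed over all missing patterns with ρ from 0.3 to 0.8, gives 4.8-5.1%, 12.6-13.5% and 27.5-29.7% wider.

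**6. Clustered gaps.** With a beta-binomial model and correlation of missingness 0.2 to 0.5, the complete diaries are 46.6-47.8, 41.8-44.5 and 34.6-39.5 of 50. The interval is then about 2-3.5%, 4-9% and 9-20% wider.

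**7. Bias illustration.** Each of the four later entries is blank with probability 2% if the 6 h score is below the overall mean, and 10% (or 20%) if above; ρ = 0.6; the same means at every visit.
- Normal scores with equal SD, true difference −0.700 SD: complete diaries give −0.692 (1% too small) or −0.658 (6% too small).
- The SAP's means and unequal SDs, true difference −9.0: about 9% or 22% too small with gamma scores, and about 11% or 28% with normal scores.
- Blanks that differ by arm only (2% against 12%), equal-SD case: −0.703, no bias beyond simulation error of about 0.003.

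In the equal-SD case, a mixed model on all observed scores gave −0.702 at both rates.

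**The case against.** **Row-wise deletion may be what was meant.** SAP section 6 says: "Python programming language and its dependent statical libraries will be used for all statistical analysis". A Python mixed model told to drop missing values removes only the blank rows. In a check with 100 subjects, nine of them with one blank, it kept 500 − 9 = 491 scores from 100 subjects; subject-wise exclusion kept 91 × 5 = 455 scores from 91. If that was the intention, no observed score is lost and only the wording needs correcting. This stands as a possibility, but naming the software does not state the rule, and the sentence names subjects.

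**Blanks may be rare.** Reminders at each time point, tracing of patients who miss follow-up and on-site collection all work against gaps. At 2% with clustered gaps the interval is only about 2-3.5% wider. This also stands: the sizes are illustrations, and 10% is an upper one.

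**Covariates.** Age is collected at diagnosis ("demographic data (age, gender) are recorded") and randomisation is stratified by molar or non-molar tooth, so the rule acts mainly on the pain scores. The SAP's covariate list is open, however. Its mention of mean change could also bring in the pre-treatment score, in which case a missing one would remove the subject under either reading. Diaries never returned are lost under either reading too.

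**Stronger readings that the documents do not support.**
- A reader might infer that SAP section 5 contradicts itself. It is better read as a general statement followed by a qualification for specific analyses; the fault is the unit of exclusion.
- A reader might infer that the trial becomes underpowered, since independent blanks above 1 − (42/50)^(1/5) = 3.4% per visit leave fewer than 42 complete diaries of 50. But no blank rate is given, the 42 rests on a 6 h t-test and not on the planned model, and SAP 2.1 says the full study will be powered from the pilot.

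**Conclusion.** The concern holds as a fault in the stated rule. Followed literally, SAP section 5 costs four observed scores for each single blank; that count needs no assumption. The pilot figures (45 scores from 9 subjects against 49 from 10) need only one blank.

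The widening of about 5%, 13% or 28-30% rests on assumed independent blank rates of 2%, 5% or 10% that are unrelated to pain, and it shrinks if gaps cluster in the same patients.

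If gaps depend on earlier observed pain, the complete-diary estimate is biased as well. The illustrations run from 1-6% of the difference with equal-SD normal scores to 9-28% with the SAP's own unequal means and SDs. A reader might infer that the loss is mainly one of precision; that range does not allow the conclusion. Nor does keeping all observed scores cure every problem: it avoids this bias only when scores are missing at random, not when a gap depends on the unrecorded pain itself.

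The point should be fixed. Confidence is high on the wording and low on the size of the harm.

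**What to change.** Replace the exclusion sentence in SAP section 5 with:

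> All randomised subjects with at least one post-operative score contribute all observed scores to the likelihood-based mixed model, by randomised group; a missing score removes only that visit, and no subject is excluded for a missing visit.

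State beside it that the analysis assumes scores are missing at random. Report unreturned diaries and diaries with gaps by arm. A complete-diary sensitivity analysis is optional.

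Do not add a rule that refits the primary model without a covariate whenever one of its values is missing, because that would let the data choose the primary model.

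The cost is low: one sentence replaced, one assumption stated and one count by arm, with no new data and no new model term. The downside is slightly more analysis work and an assumption that the data cannot verify.
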